10.1.2.2 Arm B (S-1/CDDP) [CDDP on Day 1] (Korea)

CDDP will be administered on Day 1, and S-1 will be administered orally twice daily in a administration period from Day 1 through Day 21 followed by a recovery period from Day 22 through Day 35. This regimen is to be repeated every 5 weeks until study treatment discontinuation criteria (Section 13.1.1). If S-1 administration is initiated from evening on Day 1, it will be continued until morning on Day 22, and recovery period will be from evening on Day 22 through morning on Day 36 (see Figure 10.1.2.2-1).

- A recovery period may be shortened down to 7 days after the administration period which has been finished either without AE/SAE related to study drug or with AE/SAE related to study drug that are of no safety concern and assessed as allowing the subsequent recovery period to be shortened (see Figure 10.1.2.2-2Figure 10.1.2.2-3).
- Any unused doses are not allowed to be administered in a recovery period (see Figure 10.1.2.2-3).
- If the dose interruption continues 14 days and over in the administration period, drug administration has to be discontinued in the cycle. After confirmation of being met criteria for starting new treatment cycle (see Table 10.1.3.1-2), drug administration can be restarted as the next treatment cycle (see Figure 10.1.2.2-4).
- If any of dose initiation criteria for CDDP(see Table 10.1.3.1-2) did not meet, administration of CDDP may be skipped and start each treatment cycle only with S-1.

[figure not shown]

Figure 10.1.2.2-1 Study regimen of S-1/CDDP

[figure not shown]

Figure 10.1.2.2-2 Study regimen of S-1 (1)

[figure not shown]

Figure 10.1.2.2-3 Study regimen of S-1 (2)

[figure not shown]
[figure not shown]
[figure not shown]
[figure not shown]
[figure not shown]

Figure 10.1.2.2-4 Study regimen of S-1 (3)

10.1.2.3 Arm B (S-1/CDDP) [CDDP on Day 8] (Japan)

CDDP will be administered on Day 8 (Day 6 to Day 15), and S-1 will be administered orally twice daily in a administration period from Day 1 through Day 21 followed by a recovery period from Day 22 through Day 35. This regimen is to be repeated every 5 weeks until study treatment discontinuation criteria (Section 13.1.1). If S-1 administration is initiated from evening on Day 1, it will be continued until morning on Day 22, and recovery period will be from evening on Day 22 through morning on Day 36 (see Figure 10.1.2.3-1).

- A recovery period may be shortened down to 7 days after the administration period which has been finished either without AE/SAE related to study drug or with AE/SAE related to study drug that are of no safety concern and assessed as allowing the subsequent recovery period to be shortened (see Figure 10.1.2.3-2).
- Any unused doses are not allowed to be administered in a recovery period (see Figure 10.1.2.3-3).
- If the dose interruption continues 14 days and over in the administration period, drug administration has to be discontinued in the cycle. After confirmation of being met criteria for starting new treatment cycle (see Table 10.1.3.1-2), drug administration can be restarted as the next treatment cycle (see Figure 10.1.2.3-4).
- If any of dose initiation criteria (see Table 10.1.3.1-2) for CDDP did not meet, administration of CDDP may be skipped and start each treatment cycle only with S-1.

10.1.3 Criteria for Modification of Treatment Schedule

10.1.3.1 Criteria for Dose Initiation in Each Cycle

Cycle 1 will be started after completion of the scheduled examination and the confirmation of being met all of dose initiation criteria in each cycle (Table 10.1.3.1-1, Table 10.1.3.1-2), which may be substituted by the test at randomization performed within 7 days prior to Day 1 treatment start. Cycle 2 and later cycles will be started if the results of the scheduled examination on or one day before Day 1 meet all the following criteria (Table 10.1.3.1-1, Table 10.1.3.1-2). No treatment cycle can be started if any of these criteria are not met. Even if a subject meets all the following criteria, dose initiation can be postponed at the investigator's discretion. Even if all of dose initiation criteria were met, administration of L-OHP or CDDP may be skipped and each treatment cycle can be started only with TAS-118 or S-1 at the investigator's discretion.

Table 10.1.3.1-1 Dose initiation criteria in each cycle for TAS-118 and L-OHP (Arm A)

Item	TAS-118	L-OHP
Neutrophil count	$\geq 1000 /\text{mm}^3$ (\leq Grade2) *1	$\geq 1500 /\text{mm}^3$ (\leq Grade1) *1
Platelet count	$\geq 75000 /\text{mm}^3$ (\leq Grade1) *2	
Serum creatinine*3	$< 1.5 \text{ mg/dL}$ (1.2 - $< 1.5 \text{ mg/dL}$: 1 level down)	-
Infection	No infection with fever ($< 38^\circ\text{C}$)	
Diarrhea, Stomatitis, Anorexia	\leq Grade1	
Peripheral sensory neuropathy	-	\leq Grade2*4

*1 : If the patients received G-CSF, it must be confirmed the data is obtained more than 48 hours after the last administration.

*2 : If the patients received platelet transfusion, it must be confirmed the data is obtained more than 48 hours after the last transfusion.

*3 : New treatment cycle would be initiated with creatinine clearance $\geq 50 \text{ mL/min}$, as a reference.

*4 : Even if the grade is ≤ 2 , administration of L-OHP may be skipped at the investigator's discretion.

Table 10.1.3.1-2 Dose initiation criteria in each cycle for S-1 and CDDP (Arm B)

Item	S-1	CDDP
Neutrophil count	$\geq 1000 /\text{mm}^3$ (\leq Grade2)*1	$\geq 1500 /\text{mm}^3$ (\leq Grade1)*1
Platelet count	$\geq 75000 /\text{mm}^3$ (\leq Grade1)*2	
Serum Creatinine*3	$< 1.5 \text{ mg/dL}$ (1.2 - $< 1.5 \text{ mg/dL}$: 1 level down)	$< 1.5 \text{ mg/dL}$ (1.2 - $< 1.5 \text{ mg/dL}$: 10 mg/mm^2 reduction from previous cycle)
Infection	No infection with fever ($< 38^\circ\text{C}$)	
Diarrhea, Stomatitis, Anorexia	\leq Grade1	

*1 : If the patients received G-CSF, it must be confirmed the data is obtained more than 48 hours after the last administration.

*2 : If the patients received platelet transfusion, it must be confirmed the data is obtained more than 48 hours after the last transfusion.

*3 : New treatment cycle would be started with creatinine clearance $\geq 50 \text{ mL/min}$, as a reference.

10.1.3.2 Criteria for Dose Interruption and Resumption within Treatment Cycle

The study treatment must be interrupted if any of the following dose interruption criteria (Table 10.1.3.2-1) is met during administration period of the study agent (TAS-118 or S-1), and will be resumed after the confirmation of being met all the following dose resumption criteria (Table 10.1.3.2-2). After dose resumption, the dose must be the same as before dose interruption.

Table 10.1.3.2-1 Dose interruption criteria within treatment cycle

Item	Criterion
Neutrophil count	< 1000/mm ³ (Grade 3 ≤)
Platelet count	< 50000/mm ³ (Grade 3 ≤)
Infection	Infection with fever (≥ 38°C)
Diarrhea, Stomatitis	Grade 3 ≤
Other	Difficulty in continuing treatment as assessed by the investigator (subinvestigator)

Table 10.1.3.2-2 Dose resumption criteria within treatment cycle

Item	Criterion
Neutrophil count	≥ 1000/mm ³ (≤ Grade 2)* ¹
Platelet count	≥ 50000/mm ³ (≤ Grade 2)* ²
Serum Creatinine* ³	< 1.5 mg/dL
Infection	No infection with fever (< 38°C)
Diarrhea, Stomatitis	≤ Grade 1
Other	Acceptability of resuming treatment as assessed by the investigator (subinvestigator)

*¹ : If the patients received G-CSF, it must be confirmed the data is obtained more than 48 hours after the last administration.

*² : If the patients received platelet transfusion, it must be confirmed the data is obtained more than 48 hours after the last transfusion.

*³ : The study treatment would be resumed with creatinine clearance ≥ 50 mL/min, as a reference.

10.1.3.3 Criteria for Dose Reduction (Arm A)

If the patients suffered any adverse drug reaction that meets any of the following dose reduction criteria, a new treatment cycle will be started after confirmation that the subject meets “Section 10.1.3.1 criteria for dose initiation in each cycle”, with the dose of TAS-118 or L-OHP reduced 1 level in each step according to the scheme for dose reduction criteria. Dose reduction is not allowed in the same treatment cycle.

Table 10.1.3.3-1 Dose reduction criteria for TAS-118 and L-OHP

Item	Criterion	TAS-118	L-OHP
Neutrophil count	< 500/mm ³ (Grade 4)	Worst grade observed in last cycle	1 step
Platelet count	< 25000/mm ³ (Grade 4)		1 step
Febrile neutropenia	Grade 3 ≤		1 step
Stomatitis	Grade 3 ≤		1 step
Diarrhea	Grade 3 ≤* ¹		1 step
Peripheral sensory neuropathy	Grade 3 ≤* ²		-
Serum creatinine	1.2 - < 1.5 mg/dL	The value observed before the initiation of new treatment cycle	1 step
Others* ³	Difficulty in continuing treatment without reducing the study drug dose as assessed by the investigator (subinvestigator)		

*1: In the event of a Grade 3 or greater adverse drug reaction in spite of the best treatment possible.

*2: Even if the grade is ≤ 2, the dose can be reduced at the investigator’s discretion.

*3: If the patient suffers from anorexia or other remarkable adverse drug reactions, the dose can be reduced at the investigator’s discretion.

Table 10.1.3.3-2 Dose reduction scheme for TAS-118 and L-OHP

Investigational product	Initial dose	Step 1	Step 2	Step 3
TAS-118	60 mg/dose	50 mg/dose	40 mg/dose	30 mg/dose
	50 mg/dose	40 mg/dose	30 mg/dose	None*
	40 mg/dose	30 mg/dose	None*	None*
L-OHP	85 mg/m ²	65 mg/m ²	50 mg/m ²	None*

* : In this case, the dose reduction cannot be done for the subjects, but there is no necessity that the study treatment is terminated. After confirmation that the patients meet all of dose resumption criteria, the study treatment can be restarted at minimum dose.

Table 10.1.3.3-3 Reduced dose of administration for TAS-118

Dosage in each dose	Number of sachet package	Total daily dose (Number of sachet packages)
30 mg	Morning: 1 Evening: 1	60 mg (2)
40 mg	Morning: 1 Evening: 1	80 mg (2)
50 mg	Morning: 1 Evening: 1	100 mg (2)

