10.1.3.4 Criteria for Dose Reduction (Arm B)

If the patients suffered any adverse drug reaction that meets any of the following dose reduction criteria, a new treatment cycle will be started after confirming that the subject meets “Section 10.1.3.1 criteria for dose initiation in each cycle”, with the dose of S-1 or CDDP reduced 1 level in each step according to the scheme for dose reduction criteria.

Dose reduction is not allowed in the same treatment cycle.

Table 10.1.3.4-1 Dose reduction criteria for S-1 and CDDP

Item	Criterion		S-1	CDDP
Neutrophil count	< 500/mm ³ (Grade 4)	Worst grade observed in last cycle	1 step	Reduced by 10 mg/m ²
Platelet count	< 25000/mm ³ (Grade 4)		1 step	Reduced by 10 mg/m ²
Febrile neutropenia	Grade 3 ≤		1 step	Reduced by 10 mg/m ²
Stomatitis	Grade 3 ≤		1 step	-
Diarrhea	Grade 3 ≤* ¹		1 step	-
Serum creatinine	1.2 - < 1.5 mg/dL	The value observed before the initiation of new treatment cycle	1 step	Reduced by 10 mg/m ²
Others* ²	Difficulty in continuing treatment without reducing the study drug dose as assessed by the investigator (subinvestigator)			

*1: In the event of a Grade 3 or greater adverse drug reaction in spite of the best treatment possible.

*2: If the patient suffers from anorexia or other remarkable adverse drug reactions, the dose can be reduced at the investigator’s discretion.

Table 10.1.3.4-2 Dose reduction scheme for S-1 and CDDP

Investigational product	Initial dose	Step 1	Step 2
S-1	60 mg/dose	50 mg/dose	40 mg/dose
	50 mg/dose	40 mg/dose	None*
	40 mg/dose	None*	None*
CDDP	60 mg/m ²	Reduced by 10 mg/m ²	

* : In this case, the dose reduction cannot be done for the subjects, but there is no necessity that the study treatment is terminated. After confirmation that the patients meet all of dose resumption criteria, the study treatment can be restarted at minimum dose.

Table 10.1.3.4-3 Reduced dose of administration for S-1

Dosage in each dose	Number of capsules		Total daily dose (Number of capsules)
	20 mg (white)	25 mg (orange/white)	
40 mg	Morning: 2 Evening: 2	Morning: - Evening: -	80 mg (4)
50 mg	Morning: - Evening: -	Morning: 2 Evening: 2	100 mg (4)

10.1.4 **Criteria for Dose Increase**

The dose of study drugs (TAS-118, L-OHP, S-1, and CDDP) must not be increased even after dose reduction.

10.2 **Medication and Treatments Prohibited during Study**

10.2.1 **Medication and Treatments Prohibited during Study**

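### The None* footnotes to the dose-reduction tables (Protocol 10.1.3.3 and 10.1.3.4) cite the within-cycle resumption criteria for a restart that is governed by the new-cycle initiation criteria

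*Protocol*

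**What the plan says.** The protocol has two separate sets of conditions for giving the next dose.

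- **Starting a cycle (10.1.3.1).** Tables 10.1.3.1-1 (Arm A) and 10.1.3.1-2 (Arm B) list the initiation criteria, and the text adds: "No treatment cycle can be started if any of these criteria are not met".
- **Resuming within a cycle (10.1.3.2).** Table 10.1.3.2-2 lists the resumption criteria. They apply when an interruption criterion "is met during administration period of the study agent (TAS-118 or S-1"). On the dose it says: "After dose resumption, the dose must be the same as before dose interruption".

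The dose-reduction sections use the first set. In 10.1.3.3, after a qualifying reaction, "a new treatment cycle will be started after confirmation that the subject meets" the criteria of 10.1.3.1, with the dose lowered one level. It also says: "Dose reduction is not allowed in the same treatment cycle". Section 10.1.3.4 has the same two rules for Arm B.

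The footnote to the None* cells uses the other name. It says that treatment need not be ended when no lower step exists, and then: "After confirmation that the patients meet all of dose resumption criteria, the study treatment can be restarted at minimum dose". The Arm B footnote is the same ("After confirmation that the patients meet all of dose resumption criteria"). Neither footnote gives a table number.

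**The concern.** A None* patient has just had a reaction serious enough to call for a reduction, and no reduction is available. The condition for restarting is then the main protection left, and here the protocol names a criteria set written for another situation.

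Two of the items that differ between the sets are also reasons for entering this state. Grade 4 platelets are a reduction trigger in both arms, and anorexia is named as a ground for discretionary reduction. A site that reads the footnote alone could start a cycle sooner than a site that reads 10.1.3.1. The same restart could then be classed as compliant at one site and as a deviation at another, and SAP 7.4 tabulates deviations by arm.

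**Working it through.** No sample-size, power or alpha figure is involved. The check is a comparison of text.

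**Step 1. Which set does the footnote name?** In the body of the protocol, the term dose resumption criteria belongs only to 10.1.3.2 and Table 10.1.3.2-2.

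**Step 2. When does a None* decision arise?** Reduction within a cycle is barred (10.1.3.3, 10.1.3.4), and a within-cycle resumption keeps the dose unchanged (10.1.3.2). Whether a lower step exists therefore matters only at the next cycle. The creatinine row of the reduction tables agrees, since it uses "The value observed before the initiation of new treatment cycle". Sections 10.1.2.2 and 10.1.2.3 also use restart for the next cycle after a long S-1 interruption, and there they cite Table 10.1.3.1-2.

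**Step 3. Which cells carry the footnote?**

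- Arm A: TAS-118 started at 50 mg (1 cell), TAS-118 started at 40 mg (2), L-OHP (1). Total 4.
- Arm B: S-1 started at 50 mg (1), S-1 started at 40 mg (2), CDDP (0). Total 3.

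That is 4 + 3 = 7 cells. The two consecutive cells for a 40 mg start are one patient state, so there are 3 + 2 = 5 distinct states.

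**Step 4. How do the two sets differ?**

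| Item | Initiation, TAS-118 or S-1 | Initiation, L-OHP | Resumption (Table 10.1.3.2-2) |
|---|---|---|---|
| Neutrophils (/mm3) | ≥1000 | ≥1500 | ≥1000 |
| Platelets (/mm3) | ≥75000 | ≥75000 | ≥50000 |
| Creatinine (mg/dL) | <1.5; one level down at 1.2 to <1.5 | no item | <1.5 |
| Infection with fever | none | none | none |
| Diarrhea, stomatitis | ≤ Grade 1 | ≤ Grade 1 | ≤ Grade 1 |
| Anorexia | ≤ Grade 1 | ≤ Grade 1 | no item |
| Sensory neuropathy | no item | ≤ Grade 2 | no item |
| Investigator accepts resumption | no item | no item | required |

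For the oral drug the cited set is looser on two items: platelets, by 75000 − 50000 = 25000/mm3, and anorexia. The neutrophil limit, fever, diarrhea, stomatitis and the creatinine ceiling are the same.

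**Step 5. Example.** A patient at minimum dose is recovering from Grade 4 thrombocytopenia and has 60000/mm3. That passes the platelet item of the resumption table (60000 ≥ 50000) and fails the initiation item (60000 < 75000). Section 10.1.3.1 bars the cycle.

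**Step 6. A gap on the initiation side.** At creatinine 1.2 to <1.5 mg/dL the initiation tables require the oral drug to go down one level. That cannot be done when no lower step exists, and neither set says what follows.

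**The case against.** **The footnote and 10.1.3.1 can be read together.** The footnote is permissive, waives nothing, and sits under an opening paragraph that requires the initiation criteria. Its main message is that treatment need not be terminated. For the oral drug, meeting the initiation criteria also meets every numeric and graded resumption item, so a site can satisfy both. This stands, and it is why the point is minor. It does not make the reference right.

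**The footnote might mean a mid-cycle resumption at an unchanged minimum dose.** This does not stand. Section 10.1.3.2 already covers that case, the footnote belongs to a scheme that works only between cycles, and it also marks L-OHP, which is given only on Day 1 (10.1.1.1) and cannot be resumed within a cycle.

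**Other rules limit the risk.** These are the investigator item in Table 10.1.3.2-2, the guidance in 10.2.3 on anorexia, platelets and neuropathy, the review of out-of-range laboratory values before the next dose (15.2.1), and the option to skip L-OHP (10.1.2.1). This stands.

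**Stronger readings that a reader might infer.** One is that the protocol permits a cycle below the initiation thresholds. It does not, because the prohibition in 10.1.3.1 has no exception for None* patients. Another is that patients were restarted too early, or that their number can be estimated. The documents show no affected patient and give no count of patients in a None* state. The number still progression-free under the planned accrual would not supply that count.

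**Conclusion.** The footnotes are wrong as written: they name the within-cycle criteria for a restart that is a new cycle. The size is minor. For the oral drug, the remaining risk is a site that follows the footnote alone, against 10.1.3.1 and the opening text of the same section, and starts a cycle at platelets of 50000 to <75000/mm3 or with anorexia above Grade 1. For L-OHP the cited table simply does not fit; Table 10.1.3.1-1 and the skip option in 10.1.2.1 govern it.

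The endpoint, alpha, power and primary analysis of overall survival are not affected. The conclusion rests on one assumption: that the footnotes' term carries the only meaning the protocol gives it, since they cite no table.

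**What to change.** In both footnotes, replace *dose resumption criteria* with *dose initiation criteria (Section 10.1.3.1; Table 10.1.3.1-1 for Arm A, Table 10.1.3.1-2 for Arm B)*.

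Two clarifications are optional and should stay permissive:

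- At serum creatinine 1.2 to <1.5 mg/dL, an oral drug with no lower step can be restarted at its minimum dose. CDDP has no None* cell and keeps its 10 mg/m2 reduction.
- If L-OHP does not meet its own initiation items, it may be skipped under 10.1.2.1, or the cycle may be postponed under 10.1.3.1. A mandatory skip would change the treatment rule, because 10.1.2.1 only allows skipping.

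**Cost.** The text change is two footnotes. It is not among the administrative changes exempted in 18.3, so it needs investigator agreement and IRB approval through each institution. This version is dated 07 Nov 2019 and dosing ends on 31 Jan 2020, 23 + 31 + 31 = 85 days later, so a revision would have little time to take effect. What would remain is a consistent way to classify restarts already made, and correct text for any reuse. Sites that already apply 10.1.3.1 would see no change from the replacement wording. Sites that relied on the footnote may have to delay some restarts, and that delay counts toward discontinuation after more than 28 consecutive days without study drug (13.1.1).

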10.1.3.4 Criteria for Dose Reduction (Arm B)

If the patients suffered any adverse drug reaction that meets any of the following dose reduction criteria, a new treatment cycle will be started after confirming that the subject meets “Section 10.1.3.1 criteria for dose initiation in each cycle”, with the dose of S-1 or CDDP reduced 1 level in each step according to the scheme for dose reduction criteria.

Dose reduction is not allowed in the same treatment cycle.

Table 10.1.3.4-1 Dose reduction criteria for S-1 and CDDP

Item	Criterion		S-1	CDDP
Neutrophil count	< 500/mm ³ (Grade 4)	Worst grade observed in last cycle	1 step	Reduced by 10 mg/m ²
Platelet count	< 25000/mm ³ (Grade 4)		1 step	Reduced by 10 mg/m ²
Febrile neutropenia	Grade 3 ≤		1 step	Reduced by 10 mg/m ²
Stomatitis	Grade 3 ≤		1 step	-
Diarrhea	Grade 3 ≤* ¹		1 step	-
Serum creatinine	1.2 - < 1.5 mg/dL	The value observed before the initiation of new treatment cycle	1 step	Reduced by 10 mg/m ²
Others* ²	Difficulty in continuing treatment without reducing the study drug dose as assessed by the investigator (subinvestigator)			

*1: In the event of a Grade 3 or greater adverse drug reaction in spite of the best treatment possible.

*2: If the patient suffers from anorexia or other remarkable adverse drug reactions, the dose can be reduced at the investigator’s discretion.

Table 10.1.3.4-2 Dose reduction scheme for S-1 and CDDP

Investigational product	Initial dose	Step 1	Step 2
S-1	60 mg/dose	50 mg/dose	40 mg/dose
	50 mg/dose	40 mg/dose	None*
	40 mg/dose	None*	None*
CDDP	60 mg/m ²	Reduced by 10 mg/m ²	

* : In this case, the dose reduction cannot be done for the subjects, but there is no necessity that the study treatment is terminated. After confirmation that the patients meet all of dose resumption criteria, the study treatment can be restarted at minimum dose.

Table 10.1.3.4-3 Reduced dose of administration for S-1

Dosage in each dose	Number of capsules		Total daily dose (Number of capsules)
	20 mg (white)	25 mg (orange/white)	
40 mg	Morning: 2 Evening: 2	Morning: - Evening: -	80 mg (4)
50 mg	Morning: - Evening: -	Morning: 2 Evening: 2	100 mg (4)

10.1.4 **Criteria for Dose Increase**

The dose of study drugs (TAS-118, L-OHP, S-1, and CDDP) must not be increased even after dose reduction.

10.2 **Medication and Treatments Prohibited during Study**

10.2.1 **Medication and Treatments Prohibited during Study**

The following concomitant therapies are not permitted during the study treatment period.

- (1) Any other anti-tumor therapy, including chemotherapy, radiotherapy, immunotherapy, biological response modifiers (BRMs) with antitumor effect, or endocrine therapy
- (2) Other investigational drugs
- (3) Uracil, Cimetidine and Calcium folinate
- (4) Flucytosine
- (5) Prophylactic use of G-CSF

10.2.2 **Concomitant Medications Requiring Precautions**

- (1) Warfarin potassium
Changes in coagulation profile should be monitored e.g. by INR when relevant abnormalities are indicated by other tests or findings, and the warfarin dose should be adjusted as needed.
- (2) Phenytoin
Subjects receiving phenytoin should be monitored. If abnormalities are noted, appropriate measures should be taken including dose reduction or discontinuation.
- (3) Aminoglycoside antibiotics, vancomycin hydrochloride, and furosemide (Arm B: S-1/CDDP therapy only)
- (4) Amphotericin B for injection (Arm B: S-1/CDDP therapy only)
- (5) Piretanide (Arm B: S-1/CDDP therapy only)

10.2.3 **Expected Adverse Drug Reactions and Treatment Options**

The following medications may be given concomitantly under the following guidelines. In case that dose reduction should be taken, see section 10.1.3-3 or 10.1.3-4.

- (1) Neutrophil count decrease: Appropriate measures, such as dose change (reduction) or dose interruption, should be taken. Any accompanying fever should be treated with appropriate agent (e.g. antibiotics).
- (2) Stomatitis: Severe Stomatitis interfering with continuation of oral drug treatment should be managed by appropriate measures such as dose change (reduction) or dose interruption.
- (3) Nausea/vomiting: Severe nausea/vomiting interfering with continuation of oral drug treatment should be treated by appropriate agent (e.g. antiemetics).

- (4) Anorexia: Appropriate measures, such as dose change (reduction) or dose interruption, should be taken. Taken actions for causal disease of Anorexia such as Nausea/vomitings should be taken as well.
- (5) Diarrhea: Severe diarrhea should be managed by dose interruption of TAS-118 and S-1 and appropriate fluid replacement as needed while adequately monitoring fluid and electrolyte balance. Antidiarrheal treatment (e.g. loperamide hydrochloride) should be considered while diarrhea is still mild if prevention of its exacerbation is required on the basis of careful monitoring.
- (6) Skin eruption: Skin eruption should be managed by appropriate measures such as dose reduction or dose interruption.
- (7) Platelet decrease: Appropriate measures, such as dose change (reduction) or dose interruption, should be taken.
- (8) Peripheral sensory neuropathy: Paresthesia or dysesthesia of hands, feet or area surrounding the mouth and lips (peripheral neuropathy) occurs in almost all patients from immediately after the administration of L-OHP. Carefully observe the patient's state because a constricted feeling of the larynx and pharynx (dysesthesia of the larynx and pharynx) may appear, and take appropriate measures such as dose reduction/interruption if such abnormalities occur.
- (9) Hypersensitivity: Appropriate measures, such as antihistamic agent or steroid, should be taken.
- (10) Renal disorder: Before and after treatment with CDDP, adequate hydration and coadministration of diuretics to maintain sufficient urinary volume shall be performed in order to prevent renal disorder. When renal insufficiency occurs, careful fluid management, electrolyte replacement, and if required, renal dialysis shall be performed to restore urinary volume.

